9.3.2 Method of Detecting AE, SAE and Other Reportable Safety Events

A VRC will be used by the participant to document any AEs.

9.3.3 Follow-up of AE, SAE and Other Reportable Safety Event Information

After the initial AE/SAE report, the investigator is required to proactively follow each participant at subsequent visits/contacts. All AE, SAE and other reportable safety events including pregnancy (if the participant received at least 1 vaccine dose) and exposure during breastfeeding, Cancer and Overdose will be followed until resolution, stabilization, until the event is otherwise explained, or the participant is lost to follow-up (as defined in Section 8.3). In addition, the investigator will make every attempt to follow all non-serious AEs that occur in randomized participants for outcome. Further information on follow-up procedures is given in Section 12.2 (Appendix 2: Adverse Events: Definitions and Procedures for Recording, Evaluating, Follow-up, and Reporting).

9.3.4 Regulatory Reporting Requirements for SAE

- Prompt notification (within 24 hours) by the investigator to the sponsor of SAE is essential so that legal obligations and ethical responsibilities towards the safety of participants and the safety of a study treatment under clinical investigation are met.
- The sponsor has a legal responsibility to notify both the local regulatory authority and other regulatory agencies about the safety of a study treatment under clinical investigation. All Adverse Events will be reported to regulatory authorities, IRB/IECs and investigators in accordance with all applicable global laws and regulations, ie, per ICH Topic E6 (R1) Guidelines for Good Clinical Practice.
- Investigator safety reports must be prepared for suspected unexpected serious adverse reactions (SUSAR) according to local regulatory requirements and sponsor policy and forwarded to investigators as necessary.
- An investigator who receives an investigator safety report describing an SAE or other specific safety information (eg, summary or listing of SAE) from the sponsor will file it along with the Investigator's Brochure and will notify the IRB/IEC, if appropriate according to local requirements.

9.3.5 Disease-Related Events and/or Disease-Related Outcomes not Qualifying as AEs or SAEs

Not Applicable

9.3.6 Pregnancy and Exposure During Breastfeeding

Although pregnancy and infant exposure during breastfeeding are not considered adverse events, any pregnancy or infant exposure during breastfeeding in a participant (spontaneously reported to the investigator or their designee) that occurs during the trial are reportable to the Sponsor. All reported pregnancies (in participants who received at least 1 vaccine dose) must be followed to the completion/termination of the pregnancy.

9.4 Treatment of Overdose

In this study, an overdose is defined as a participant receiving >3 doses (0.5 mL each dose), or receiving ≥ 0.75 mL of 9vHPV vaccine in any one dose.

Decisions regarding dose interruptions or modifications will be made by the investigator in consultation with the Sponsor Clinical Director based on the clinical evaluation of the participant.

9.5 Safety

Details regarding specific safety procedures/assessments to be performed in this study are provided below.

Planned time points for all safety assessments are provided in the SoA.

9.5.1 Patient Reported Outcome

Adverse events will be documented using a validated VRC.

All participants will receive a VRC at the Day 1, Month 2, and Month 6 study vaccination visits. Using the VRC, the participant or the parent/guardian of the participant will be asked to record the participant's oral temperature in the evening after each study vaccination and daily for 4 days after each study vaccination for the purpose of identifying febrile events. Also, beginning after each study vaccination and for a total of 15 days including the day of vaccination, the participant will be asked to record injection-site and systemic AEs, concomitant medications, and concomitant vaccinations by means of the VRC.

Serious AEs, cancers and overdoses, pregnancy information, lactation information, and infant SAEs will also be collected for the entire duration of the study as described in Section 9.3. In addition, new medical conditions not present at baseline and not reported as an adverse experience will be collected throughout the study.

9.5.2 Pregnancy Testing

All female participants will have a serum or urine pregnancy test (sensitive to 25 mIU/mL β -hCG) performed at each vaccination visit (ie, Day 1, Month 2, or Month 6) and at Month 7 per the manufacturer's instructions. All materials used for serum and/or urine pregnancy testing will be provided by the study sites.

The pregnancy test results must be obtained prior to each study vaccination (on the day the participant is vaccinated). Any participant found to be pregnant at Day 1 will not be allocated and will not participate in the study. For randomized participants who become pregnant after receiving one or two study vaccinations, study visits and vaccinations will be paused until resolution of the pregnancy (eg, term, elective termination, spontaneous abortion). Study visits and study vaccination in pregnancy participants will be handled as described in [Table 3](#).

Table 3 Guidelines for Pregnant Participants: Managing Study Visits and Study Vaccinations

Time When Pregnancy is Detected	Action
Day 1 (before first vaccination)	Do not enroll.
Between Day 1 and Month 2 (After study vaccine dose 1 and before study vaccine Dose 2 was administered)	
 • No scheduled visits until resolution of the pregnancy (eg, term, elective termination, spontaneous abortion). • The Month 2 study vaccination should be administered at least 4 weeks following resolution of pregnancy and after normalization of β-hCG levels. • The Month 6 study vaccination should be administered 4 months after the Month 2 study vaccination. • The Month 7 visit should be conducted 1 month after the Month 6 study vaccination.
Between Month 2 and Month 6 (After study vaccine dose 2 and before study vaccine Dose 3 was administered)	
 • No scheduled visits until resolution of the pregnancy (eg, term, elective termination, spontaneous abortion). • The Month 6 study vaccination should be administered at least 4 weeks following resolution of pregnancy and after normalization of β-hCG levels. • The Month 7 visit should be conducted 1 month after the Month 6 study vaccination.
After Month 6 (After study vaccine Dose 3 was administered)	
 • Continue with scheduled study visits during the pregnancy. • Safety follow-up will be conducted after resolution of the pregnancy (eg, term, elective termination, spontaneous abortion).

β -hCG=beta human chorionic gonadotropin.

Management of pregnant participants will be as follows. All female participants undergo pregnancy testing based on urine or serum analyses for β -hCG at each study visit (Section 2: SoA). Participants found to be pregnant at Day 1 are not eligible to participate in the study (Section 6.2: exclusion criterion 14). Female participants 16 years and older enrolled in the study are instructed to use effective contraception through Month 7 (Section 6.1: inclusion criterion 7). Participants who inadvertently become pregnant before receiving all 3 doses of vaccine do not receive additional doses until ≥ 4 weeks after resolution of pregnancy and normalization of β -hCG levels as described in Table 3. Breastfeeding is not a contraindication to enrollment or to receiving study vaccinations.

Pregnancy and breastfeeding in study participants and infant SAEs for all infants born to participants who received the study vaccine or who were breastfed during the study must be reported.

9.5.3 Post-vaccination Observation Period (30 minutes)

All participants will be observed for at least 30 minutes after each study vaccination for any untoward effects, including allergic reactions. This observation period will be documented in the participant's study chart.

9.5.4 Clinical Laboratory Assessments

Refer to Section 12.3 (Appendix 3: Clinical Laboratory Tests) for the list of clinical laboratory tests to be performed and to the SoA for the timing and frequency.

- All protocol-required laboratory assessments, as defined in Section 2 (SoA), must be conducted in accordance with the manufacturer's specifications.
- If laboratory values from non-protocol specified laboratory assessments performed at the institution's local laboratory require a change in study participant management or are considered clinically significant by the investigator (eg, SAE or AE or dose modification), then the results must be recorded in the appropriate CRF (eg, SLAB).
- The investigator must review the laboratory report, document this review, and record any clinically relevant changes occurring during the study. The laboratory reports must be filed with the source documents.
- For any laboratory tests with values considered clinically significantly abnormal during participation in the study or within 15 days after the last dose of study treatment, repeat assessments may be performed as determined by the investigator.

9.6 Pharmacokinetics

Pharmacokinetic parameters will not be evaluated in this study.

9.7 Pharmacodynamics

Pharmacodynamic parameters will not be evaluated in this study.

9.8 Biomarkers

Biomarkers are not evaluated in this study.

9.9 Visit Requirements

Visit requirements are outlined in Section 2 (SoA). Specific procedure-related details are provided above in Section 9 (Study Assessments and Procedures).

9.9.1 Prerequisites for Vaccination Visits

This section summarizes prerequisites for visits with study vaccinations and specimen collection. Deviations from these prerequisites require consultation between the investigator and the Sponsor and written documentation of the collaborative decision. See the Administrative Binder for a summary of deviations that require documentation in this study.

See the inclusion/exclusion criteria for specific restrictions at Day 1. For visits with study vaccinations, study personnel should verify by questioning the participant and/or by examination that:

1. The participant has not had a fever (defined as an oral temperature of $\geq 100.0^{\circ}\text{F}$ or $\geq 37.8^{\circ}\text{C}$) within the 24-hour period prior to any study vaccination visit.
2. The participant has not received any systemic (oral or parenteral) corticosteroids in the 2 weeks prior to the Month 2 and Month 6 study vaccination visits.
3. The participant has not received a nonstudy inactive or recombinant vaccine within 14 days prior to any study vaccination visit or a nonstudy live vaccine within 21 days prior to any study vaccination visit.
4. The participant is not pregnant as confirmed by a serum or urine pregnancy test.

If the participant does not meet the requirements listed above, the study visit (including specimen collection and study vaccination) should be rescheduled.

9.9.2 Discontinued Participants Continuing to be Monitored in the Study

Participants who discontinue study vaccinations but continue in the study may attend study visits per the study flow chart (SoA table). However, serum will not be collected at the Month 7 study visit from participants who did not complete the 3-dose vaccination regimen.

10. Statistical Analysis Plan

This section outlines the statistical analysis strategy and procedures for the study. If, after the study has begun, but prior to the final database lock, changes are made to the primary hypothesis, or the statistical methods related to those hypothesis, then the protocol will be amended (consistent with ICH Guideline E-9). Changes to exploratory or other non-confirmatory analyses made after the protocol has been finalized, but prior to final database lock, will be documented in a supplemental Statistical Analysis Plan and referenced in the Clinical Study Report (CSR) for the study. Post hoc exploratory analyses will be clearly identified in the CSR.

10.1 Statistical Analysis Plan Summary

This section contains a brief summary of the statistical analyses for this study. Full details are provided in the following sections.

Study Design Overview	A Phase III open-label, safety, and immunogenicity study of a 9vHPV vaccine administered to 9- to 26-Year-Old Females and Males in Vietnam
Treatment Assignment	Single-arm, open-label, 9vHPV vaccine administration with 1:1 allocation ratio among 9- to 15- and 16- to 26-year-old participants. The study will recruit females and males, with 2:1 enrollment ratio within each age group.
Analysis Populations	Immunogenicity: Per-Protocol Immunogenicity (PPI)
	Safety: All Participants as Treated (APaT)
Primary Endpoint	Percent of participants who seroconverted to HPV Types 6, 11, 16, 18, 31, 33, 45, 52, and 58 at 4 weeks post Dose 3.
Key Secondary Endpoints	Immunogenicity: GMTs of HPV Types 6, 11, 16, 18, 31, 33, 45, 52, and 58 at 4 weeks post Dose 3.
	Safety: Number (and proportion) of participants with the following: vaccine-related SAEs and any SAE (occurring at any time during the study); injection-site AEs, systemic AEs, and discontinuations due to an AE within Day 1 to Day 15 following receipt of 9vHPV vaccination; and, oral temperatures within Day 1 to Day 5 following receipt of 9vHPV vaccination.
Statistical Methods for Key Immunogenicity Analysis	The primary immunogenicity hypothesis will be addressed by calculating point and 95% CI estimates of percent seroconversion based on the exact binomial method of Clopper and Pearson [Clopper, C. J. and Pearson, E. S. 1934].
	The secondary immunogenicity objective will be addressed by calculating point and 95% CI estimates of GMTs based on the t-distribution.
Statistical Methods for Key Safety Analyses	Safety assessments will be descriptive in nature and will include calculation of proportions of participants with adverse events.
Interim Analyses	No interim analyses are planned for this study.
Multiplicity	No multiplicity adjustment is planned as successful demonstration of the primary immunogenicity hypothesis requires the lower limit of the 95% CI of percent seroconversion be >90% of all 9 HPV Types 6, 11, 16, 18, 31, 33, 45, 52, and 58.

Sample Size and Power	The planned sample size of 200 participants to be vaccinated with 9vHPV vaccine provides ~97% power at an overall 1-sided Type I error equal to 0.025 to establish that the 9vHPV vaccine induces among participants >90% seroconversion to HPV Types 6, 11, 16, 18, 31, 33, 45, 52, and 58 at 4 weeks post Dose 3.
-----------------------	---

10.2 Responsibility for Analyses/In-House Blinding

The statistical analysis of the data obtained from this study will be the responsibility of the Clinical Biostatistics department of the Sponsor.

This study is being conducted as a non-randomized, open-label study (ie, participants, investigators, and Sponsor personnel will be aware of participant treatment assignments after each participant is enrolled and treatment is assigned).

The Clinical Biostatistics department will generate the allocation schedules for study treatment assignment. Treatment allocation will be implemented via an IRT.

10.3 Hypotheses/Estimation

Objectives and hypothesis of the study are stated in Section 4.

10.4 Analysis Endpoints

10.4.1 Immunogenicity Endpoints

The primary immunogenicity endpoints are the seroconversion percentages to each of HPV 6, 11, 16, 18, 31, 33, 45, 52, and 58 by 4 weeks post Dose 3. Seroconversion is defined as changing a participant's serostatus from seronegative at Day 1 to seropositive by 4 weeks post Dose 3. A participant with anti-HPV cLIA titer at or above the serostatus cutoff for a given HPV type is considered seropositive for that HPV type.

The secondary immunogenicity endpoints are GMTs to HPV 6, 11, 16, 18, 31, 33, 45, 52, and 58 at 4 weeks post Dose 3.

10.4.2 Safety Endpoints

The safety endpoints are the number (and proportions) of participants who reported injection-site AEs, systemic AEs, and discontinuations due to an AE within Day 1 to Day 15 following receipt of 9vHPV vaccination. In addition, SAEs occurring at any time during the study and oral temperatures (reported Day 1 to Day 5 following any vaccination) will be summarized.

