8.1 Discontinuation of Study Treatment

Discontinuation of study treatment does not represent withdrawal from the study.

As certain data on clinical events beyond study treatment discontinuation may be important to the study, they must be collected through the participant's last scheduled follow-up, even if the participant has discontinued study treatment. Therefore, all participants who discontinue study treatment prior to completion of the third vaccination will still continue to participate in the study as specified in Section 2 (SoA) and Section 9.10.2 (Discontinued Participants Continuing to be Monitored in the Study). Whenever possible, when a participant discontinues/withdraws prior to study completion, all applicable activities scheduled for the final study visit should be performed at the time of discontinuation except for serum collection for HPV testing. The final visit assessments can be done via a phone call and the VRC.

Participants may discontinue study treatment at any time for any reason or be dropped from the study treatment at the discretion of the investigator should any untoward effect occur. In addition, a participant may be discontinued from study treatment by the investigator or the Sponsor if study treatment is inappropriate, the study plan is violated, or for administrative and/or other safety reasons. Specific details regarding procedures to be performed at study treatment discontinuation are provided in Section 9.1.9 (Discontinuation and Withdrawal).

A participant must be discontinued from study treatment but continue to be monitored in the study for any of the following reasons:

- The participant or participant's legally acceptable representative requests to discontinue study treatment.

For participants who are discontinued from study treatment but continue to be monitored in the study, all visits and procedures, as outlined in the SoA, should be completed.

Participants may be allowed to begin study treatment again if deemed medically appropriate, with consultation from the Clinical Director.

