9.1.8.3 Timing of Dose Administration

Vaccination will be administered at the following time points: Day 1, Month 2, and Month 6.

Acceptable day ranges for vaccination visits are as follows:

- Dose 1: Day 1 (±0 days)
- Dose 2: Month 2 (±3 weeks)
- Dose 3: Month 6 (±4 weeks)

The Day 1 visit is defined as the day that the first study vaccination is given (ie, date when Dose 1 of 9vHPV vaccine is injected).

The visit windows described here are for site scheduling purposes. The visit windows used for exclusion from the statistical analyses are provided in Section 10.5.1.

For post-Day 1 vaccinations, the day ranges for inclusion in the statistical analysis are wider than the protocol specified visit windows primarily to account for differences at the sites in counting months (eg, 1 calendar month versus 30 days versus 4 weeks).

To calculate visit windows, assume 1 month equals 30 days and 1 week equals 7 days.

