9.3 Adverse Events (AE), Serious Adverse Events (SAE) and Other Reportable Safety Events

The definitions of an adverse event (AE) or serious adverse event (SAE), as well as the method of recording, evaluating, and assessing causality of AE and SAE and the procedures for completing and transmitting AE, SAE and other reportable safety event reports can be found in Section 12.2 (Appendix 2: Adverse Events: Definitions and Procedures for Recording, Evaluating, Follow-up, and Reporting).

AE, SAEs, and other reportable safety events will be reported by the participant (or, when appropriate, by a caregiver, surrogate, or the participant's legally authorized representative).

The investigator, who is a qualified physician, and any designees are responsible for detecting, assessing, documenting, and reporting events that meet the definition of an AE or SAE as well as other reportable safety events. Investigators remain responsible for following up AE, SAEs and other reportable safety events for outcome according to Section 9.3.3.

9.3.1 Time Period and Frequency for Collecting AE, SAE and Other Reportable Safety Event Information

All AEs, SAEs and other reportable safety events that occur after the consent form is signed but before allocation/randomization must be reported by the investigator if they cause the participant to be excluded from the study, or are the result of a protocol-specified intervention, including but not limited to washout or discontinuation of usual therapy, diet, placebo treatment or a procedure.

From the time of allocation/randomization through 14 days following the first vaccination(s) and from the time of any subsequent vaccination(s) through 14 days thereafter, all AEs, SAEs and other reportable safety events must be reported by the investigator.

Additionally, any SAE brought to the attention of an investigator at any time outside of the time period specified in the previous paragraph also must be reported immediately to the Sponsor if the event is either:

1. A death that occurs prior to the participant completing the study, but outside the time period specified in the previous paragraph.
2. An SAE is an AE that is considered by an investigator who is a qualified physician to be vaccine related.

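### AE discontinuations are limited to Day 1 to Day 15 without saying whether the window dates the AE or the stop, and no whole-study count is planned

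*Combined protocol and SAP*

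**What the plan says.** Three sections of the combined protocol and SAP carry the same restriction.

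- Section 10.1 lists among the key secondary safety endpoints "injection-site AEs, systemic AEs, and discontinuations due to an AE within Day 1 to Day 15 following receipt of 9vHPV vaccination".
- Section 10.4.2 defines the safety endpoints with the same window: "discontinuations due to an AE within Day 1 to Day 15 following receipt of 9vHPV vaccination".
- Section 10.6.2 repeats it at the end of a longer list of proportions that also names SAEs and vaccine-related SAEs.

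Sections 10.1 and 10.4.2 give SAEs a different window, namely any time during the study. No section gives discontinuations a whole-study window.

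The 15 days match how AEs are collected. In Section 9.5.1 the report card runs "for a total of 15 days including the day of vaccination". In Section 9.3.1, after each later dose, "through 14 days thereafter, all AEs, SAEs and other reportable safety events must be reported by the investigator". Outside those periods, Section 9.3.1 still requires deaths and vaccine-related SAEs to be reported. Section 9.5.1 says SAEs are collected for the whole study.

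On stopping, Section 8.1 says "Participants may discontinue study treatment at any time for any reason". Section 10.11 tabulates how many participants receive each dose and specifies no breakdown by reason for a missed dose.

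**The concern.** A 15-day window is a sensible limit for diary-reported reactions. A discontinuation is a different kind of event, because the AE and the decision to stop can lie weeks apart. In this schedule the next opportunity to decline a dose comes about two months after Dose 1 and about four months after Dose 2.

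The phrase can be read in two ways, and each leaves some AE discontinuations out of the count. No other planned table would show them with their reason. In a single-arm study of 200 participants such events are likely to be few, so one or two omissions could change what is reported. An omission can only lower the count.

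**Working it through.** The documents state no expected number or rate of AE discontinuations, so there is no plan figure to reproduce. The check is day arithmetic on the visit windows, followed by a comparison of the two readings.

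**Inputs**

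- The counting window closes on Day 15. With the day of vaccination as Day 1 (the diary convention in Section 9.5.1), that is 14 days after the dose.
- Scheduling windows, Section 9.1.8.3: "Dose 2: Month 2 (±3 weeks" and "Dose 3: Month 6 (±4 weeks", each with a closing bracket in the text.
- Day counting, same section: "To calculate visit windows, assume 1 month equals 30 days and 1 week equals 7 days".
- Analysis ranges, Table 4 in Section 10.5.1: Dose 2 at 36 to 84 days and Dose 3 at 148 to 218 days after Dose 1.

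**Visit timing**

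- Dose 2 by scheduling window: 2 × 30 ± 3 × 7 = 60 ± 21, so 39 to 81 days after Dose 1.
- Dose 3 by scheduling window: 6 × 30 ± 4 × 7 = 180 ± 28, so 152 to 208 days after Dose 1.
- Shortest interval from Dose 2 to Dose 3: 152 − 81 = 71 days by the scheduling windows, and 148 − 84 = 64 days by Table 4.

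| Gap from close of the window to the next dosing visit | Scheduling, earliest | Table 4, earliest | Nominal |
|---|---|---|---|
| After Dose 1 | 39 − 14 = 25 days | 36 − 14 = 22 days | 60 − 14 = 46 days |
| After Dose 2 | 71 − 14 = 57 days | 64 − 14 = 50 days | 120 − 14 = 106 days |

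On these ranges no later dosing visit can fall inside the preceding Day 1 to Day 15 window.

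**Reading A: the window dates the discontinuation.** A participant who has a reaction on Day 3 and whose stop is recorded at the Month 2 visit is not counted. If f is the fraction of AE discontinuations dated after Day 15, the share missed equals f. The documents give no value for f, so the range is 0% to 100%.

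**Reading B: the window dates AE onset.** The same participant is counted. What drops out is a stop caused by an AE that began after Day 15. If that AE is a vaccine-related SAE, it is reportable under Section 9.3.1 and enters the whole-study SAE summary, while the stop it caused is absent from the discontinuation count. The documents give no value for this fraction either.

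**Weight of one event.** If all 200 participants are in the safety population (assumption), each omitted discontinuation changes the reported proportion by 1/200 = 0.5 percentage points.

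**The case against.** The strongest reply is that reading B is the natural one. The window matches the 15-day diary and the 14-day reporting period, and in the same sentence of Section 10.4.2 it governs injection-site and systemic AEs, where it can only mean when the AE occurred. On that reading a dose declined at Month 2 because of a Day 3 reaction is counted. This stands, and it makes the likely loss smaller.

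Second, Section 8.1 lets a participant stop at any time, so nothing ties a stop, or its recorded date, to a dosing visit. This also stands. From the long gaps between doses a reader might infer that the endpoint misses most AE discontinuations, or that the rate is pulled toward zero. The documents do not support either inference: they give no timing for such stops, and claiming most would need f above 50%.

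Third, late SAEs are not lost, because they are summarized anyway, and at the 0.04% rate cited in Section 10.9.2 the chance of even one vaccine-related SAE among 200 is 1 − (1 − 0.0004)^200 = 7.7%. That is correct, but it bounds only one class of late event. A stop can also follow an unrelated SAE or a non-serious AE.

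Fourth, discontinuation is absent from the Section 4 safety endpoints, and the safety analysis is descriptive. True, but Section 10.1 lists it as a key secondary safety endpoint. The doses-received table in Section 10.11 would reveal a missed dose without its cause.

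After Dose 3 no study dose remains to be stopped, so only study withdrawal could be affected there.

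**Conclusion.** The point holds as a defect in the definition of a listed safety measure. The three sections impose a window without stating what it dates, and neither reading captures every AE discontinuation. Under reading A the exclusion of stops recorded at the next dosing visit is certain, because the closest such visit is 25 days (scheduling) or 22 days (Table 4) after the window closes. Under reading B, which fits the rest of the plan better, only stops caused by an AE or SAE starting after Day 15 are dropped.

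The size is unknown. The share missed lies between 0% and 100% and may well be small. The arithmetic assumes visits within the stated ranges and the day of vaccination counted as Day 1. No hypothesis test or immunogenicity conclusion is affected. This is a cheap improvement.

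**What to change.** In Sections 10.1, 10.4.2 and 10.6.2, replace the windowed item with a count and proportion of participants who discontinued vaccination or the study because of an AE at any time from Dose 1 through Month 7. Show as a subset those whose AE began on Day 1 to Day 15 after a vaccination. This settles what the window dates and keeps the figure that reading B would have produced. In Section 10.6.2, place the any-time items apart from the windowed ones, so that the 15-day limit cannot be read as also covering SAEs.

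The cost is wording in three sections and one added table row. No new data should be needed, since the endpoint as planned already requires knowing that an AE was the reason for stopping. No rule on when or why vaccination is stopped changes. The one drawback is that non-serious AEs starting after Day 15 are not systematically collected, so they would be known only through the discontinuation reason. A footnote to the table should say so.
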